3.6 Post Study Drug Study Follow up

Subjects who discontinue study drug may continue to be followed.

Subject's contact information will be collected/confirmed throughout the study so that subjects who discontinue study drug may continue to be followed for resolution of a pregnancy or SAE.

3.6.1 Withdrawal of Consent

Subjects who request to discontinue study drug will remain in the study and must continue to be followed for protocol specified follow-up procedures. The only exception to this is when a subject specifically withdraws consent for any further contact with him/her or persons previously authorized by subject to provide this information. Subjects should notify the investigator of the decision to withdraw consent from future follow-up **in writing**, whenever possible. The withdrawal of consent should be explained in detail in the medical records by the investigator, as to whether the withdrawal is from further treatment with study drug only or also from study procedures and/or post treatment study follow-up, and entered on the appropriate CRF page. In the event that vital status (whether the subject is alive or dead) is being measured, publicly available information should be used to determine vital status only as appropriately directed in accordance with local law.

3.6.2 Lost to Follow-Up

All reasonable efforts must be made to locate subjects to determine and report their ongoing status. This includes follow-up with persons authorized by the subject as noted above. Lost to follow up is defined by the inability to reach the subject after a minimum of three documented phone calls, faxes, or emails as well as lack of response by subject to one registered mail letter.

All attempts should be documented in the subject's medical records. If it is determined that the subject has died, the site will use permissible local methods to obtain the date and cause of death.

If investigator's use of third-party representative to assist in the follow-up portion of the study has been included in the subject's informed consent, then the investigator may use a Sponsor-retained third-party representative to assist site staff with obtaining subject's contact information or other public vital status data necessary to complete the follow-up portion of the study. The site staff and representative will consult publicly available sources, such as public health registries and databases, in order to obtain updated contact information. If after all attempts, the subject remains lost to follow-up, then the last known alive date as determined by the investigator should be reported and documented in the subject's medical records.

4 STUDY DRUG

Study drug includes both Investigational [Medicinal] Product (IP/IMP) and Non-investigational [Medicinal] Product (Non-IP/Non-IMP) and can consist of the following:

Table 4-1: Study Drugs for AI468048:

Product Description / Class and Dosage Form	Potency	IMP/Non-IMP	Blinded or Open Label	Packaging/ Appearance	Storage Conditions (per label)
BMS-955176	60 mg ^a	IMP	Open Label	Bottle/ A white to off-white, biconvex, oval shaped film coated tablet	Store at 2 - 30°C Protect from light. Store in a tightly closed container.
BMS-955176	120 mg ^a	IMP	Open Label	Bottle/ A white to off-white, biconvex, capsule shaped tablet	Store at 2 - 30°C Protect from light. Store in a tightly closed container.
Tenofovir (TDF)	300 mg	Non-IMP	Open Label	Various packaging configurations	Refer to label on container or package insert.
Atazanavir (ATV)	200 mg	IMP	Open Label	Bottle/ Blue cap and blue body printed with white ink	Store at 15 - 30°C Store in a tightly closed container.
Atazanavir (ATV)	300 mg	IMP	Open Label	Bottle/ Red cap and blue body, printed with white ink	Store at 15 - 30°C Store in a tightly closed container.
Ritonavir (RTV)	100 mg	Non-IMP	Open Label	Various packaging configurations	Refer to label on container or package insert.
Dolutegravir (DTG)	50 mg	Non-IMP or IMP, depending on country approval status.	Open Label	Various packaging configurations	Refer to label on container or package insert.

^a The 180 mg dose of BMS-955176 will be constructed with BMS-955176 60 mg + BMS-955176 120 mg

4.1 Investigational Product

An investigational product, also known as investigational medicinal product in some regions, is defined a pharmaceutical form of an active substance or placebo being tested or used as a reference in a clinical study, including products already with a marketing authorization but used or assembled (formulated or packaged) differently than the authorized form, or used for an unauthorized indication, or when used to gain further information about the authorized form.

The investigational product should be stored in a secure area according to local regulations. It is the responsibility of the investigator to ensure that investigational product is only dispensed to study subjects. The investigational product must be dispensed only from official study sites by authorized personnel according to local regulations.

In this protocol, investigational product(s) is/are: BMS-955176, ATV, and DTG (in countries where DTG has not been approved for use). These products will be supplied.

4.2 Non-investigational Product

Other medications used as support or escape medication for preventative, diagnostic, or therapeutic reasons, as components of the standard of care for a given diagnosis, may be considered as non-investigational products.

In this protocol, noninvestigational product(s) is/are: TDF, RTV, and DTG (in countries where DTG is approved for use). These products will be supplied.

4.3 Storage and Dispensing

The product storage manager should ensure that the study drug is stored in accordance with the environmental conditions (temperature, light, and humidity) as determined by BMS. If concerns regarding the quality or appearance of the study drug arise, the study drug should not be dispensed and contact BMS immediately.

Study drug not supplied by BMS will be stored in accordance with the package insert.

Investigational product documentation (whether supplied by BMS or not) must be maintained that includes all processes required to ensure drug is accurately administered. This includes documentation of drug storage, administration and, as applicable, storage temperatures, reconstitution, and use of required processes (eg, required diluents, administration sets).

Storage facilities for controlled substances must be securely locked and substantially constructed, with restricted access to prevent theft or diversion, as applicable by local regulations.

4.4 Method of Assigning Subject Identification

At the start of the screening period, the investigative staff will call the Assignment Center via an Interactive Voice Response System ([IVRS], or its web-based equivalent) designated by the sponsor to enroll the subject and to obtain a subject patient identification number (PID).

For subjects who meet the protocol eligibility criteria, the investigative staff will call the IVRS and subjects will start treatment.

Subjects will be randomly assigned in the staged fashion to one of the treatment arms, and stratified by HIV-1 Clade (AE versus Other), as described in [Section 3](#) and as outlined in the AI468048 Study Schematic [Figure 3.1.6-1](#).

Note: All efforts should be made to limit the possibility of randomizing subjects that do not start treatment. If a subject is randomized but does not receive study medication, the BMS study team must be notified immediately.

4.5 Selection and Timing of Dose for Each Subject

Subjects will be randomized into the treatment arms in a staged fashion described in [Section 3.1](#).

Stage 1:

In Stage 1, subjects will be randomly assigned 1:1 to one of two treatment arms and on Day 1 will begin dosing with:

- Arm 1 : BMS-955176 120 mg QD + ATV/r 300/100 mg QD + DTG 50 mg QD, or
- Arm 2: TDF 300 mg QD + ATV/r 300/100 mg QD + DTG 50 mg QD

Stage 2:

In Stage 2, subjects will be randomly assigned 1:1:1 to one of three treatment arms and on Day 1 will begin dosing with:

- Arm 3: BMS-955176 120 mg QD + ATV 400 mg QD + DTG 50 mg QD, or
- Arm 4: BMS-955176 180 mg QD + ATV 400 mg QD + DTG 50 mg QD, or
- Arm 5: TDF 300 mg QD + ATV/r 300/100 mg QD + DTG 50 mg QD

4.5.1 Instructions for Dose Administration

4.5.1.1 General Instructions

- Subjects should administer doses of each drug from only one bottle at a time, until that bottle is empty, before another bottle may be opened.
- Subjects will be required to complete Dosing Diaries so that drug administration can be accurately accounted. It is important that sites provide instructions to subjects for completion and obtain their acknowledgment that doing so provides critical information for the clinical trial.
- Dosing times (and study appointment times) must be carefully considered through Week 24 due to the requirements of the PK collection outlined in [Section 5.5](#).

4.5.1.2 Specific Dosing Instructions for Initial Treatment Arm Assignment

In the morning, with a meal, subjects will take the following:

- Arm 1: One pill each from bottles BMS-955176 120 mg, ATV, RTV, and DTG
- Arm 2: One pill each from bottles TDF, ATV, RTV and DTG

- Arm 3: One pill each from bottles BMS-955176 120 mg, DTG, and two pills from bottle ATV (the unboosted dose of ATV is 400 mg, achieved by 200 mg x 2)
- Arm 4: One pill each from bottles BMS-955176 60 mg, BMS-955176 120 mg and DTG, and two pills from bottle ATV (the unboosted dose of ATV is 400 mg, achieved by 200 mg x 2)
- Arm 5: One pill each from bottles TDF, ATV, RTV and DTG

4.5.2 Dose Modifications

No dose adjustments or changes in intake frequency are allowed for any of the assigned study drugs in the protocol, except for the unique case of treatment-limiting renal toxicity which limits the use of the TDF. In the event of treatment-limiting renal toxicity, dose interval adjustments for TDF are permitted according to the local package insert/label, and only after the completion of the Week 2 Intensive PK optional Visit, if the subject is inclined to participate.

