The confidentiality of records that could identify subjects must be protected, respecting the privacy and confidentiality rules applicable to regulatory requirements, the subjects' signed ICF and, in the US, the subjects' signed HIPAA Authorization.

The consent form must also include a statement that BMS and regulatory authorities have direct access to subject records.

Subjects unable to give their written consent (eg, stroke or subjects with or severe dementia) may only be enrolled in the study with the consent of a legally acceptable representative. The subject must also be informed about the nature of the study to the extent compatible with his or her understanding, and should this subject become capable, he or she should personally sign and date the consent form as soon as possible. The explicit wish of a subject who is unable to give his or her written consent, but who is capable of forming an opinion and assessing information to refuse participation in, or to be withdrawn from, the clinical study at any time should be considered by the investigator.

The rights, safety, and well-being of the study subjects are the most important considerations and should prevail over interests of science and society.

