3.1.3 Week 2 Intensive PK Visit

Subjects with anemia, defined as Hemoglobin < 11.0 g/dL, should be excluded from participation in the Week 2 Intensive PK Substudy.

Subjects in all arms will have the opportunity to participate in an elective Intensive PK Substudy visit at Week 2 (window for visit: Day 12-16). Approximately 60 subjects, 12 subjects from each arm, are expected to participate in the substudy; BMS may allow the substudy to over-enroll in an effort to have a sufficient number of complete datasets.

The series of 12 blood draws begins with pre-dose (0-hour) blood samples to be collected approximately 24 hours (20-28 hrs) after the morning doses of study drugs that were taken on the day before. Ten more samplings are drawn through the 12-hr time point, with one final sampling collected at the 24-hr time point, requiring the subject to either remain overnight in the clinic, or to return the next morning; the final 24-hr sample will be collected prior to administration of the morning doses of study drugs (See [Section 5.5.1](#)).

PK Tools/Job Aids will be provided to assist with the proper sequencing of dosing and blood sample collections, as well as the collection of required data.

3.1.4 Visits Week 4 - 96

Subjects are expected to be treated for the duration of 96 weeks. In each Stage, after Day 1 and the optional Intensive PK visit at Week 2, subjects will be required to attend 12 more in-clinic study visits over the 96-week treatment period, as follows:

- Visits are conducted every 4 weeks from Week 4 through Week 16
- Visits are conducted every 8 weeks from Week 24 through Week 48
- Visits are conducted every 12 weeks from Week 60 through Week 96

Visits should be scheduled as an interval from the Day 1/Randomization date, and within a window of 5 days earlier or later.

One of the visits Week 4 - 24 should meet the very specific timing requirements as outlined in [Section 5.5.2](#) for a pre-AM dose blood collection.

Telephonic visits will be conducted with each subject at visit Weeks 20, 28, 36, 44, 54, 66, 78, and 90 to conduct an adherence assessment and to continue retention efforts

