6.2.1 Nonserious Adverse Event Collection and Reporting

The collection of nonserious AE information should begin at initiation of study drug. Nonserious AE information should also be collected from the start of a placebo lead-in period or other observational period intended to establish a baseline status for the subjects.

Nonserious AEs should be followed to resolution or stabilization, or reported as SAEs if they become serious (see [Section 6.1.1](#)). Follow-up is also required for nonserious AEs that cause interruption or discontinuation of study drug and for those present at the end of study treatment as appropriate. All identified nonserious AEs must be recorded and described on the nonserious AE page of the CRF (paper or electronic).

Completion of supplemental CRFs may be requested for AEs and/or laboratory abnormalities that are reported/identified during the course of the study.

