6.3 Laboratory Test Result Abnormalities

The following laboratory test result abnormalities should be captured on the nonserious AE CRF page or SAE Report Form (paper or electronic) as appropriate:

- Any laboratory test result that is clinically significant or meets the definition of an SAE
- Any laboratory test result abnormality that required the subject to have study drug discontinued or interrupted
- Any laboratory test result abnormality that required the subject to receive specific corrective therapy

It is expected that wherever possible, the clinical rather than laboratory term would be used by the reporting investigator (eg, anemia versus low hemoglobin value).

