6.7.1 Toxicity Management

6.7.1.1 Management of Elevations in Liver Transaminases

The following Table 6.7.1.1-1 summarizes the management of elevations in liver transaminases:

Table 6.7.1.1-1: Management of Elevations in Liver Transaminases Grade Level of AST or ALT Recommendations^a

Grade	Recommendation
Grade 1	None
Grade 2	none
Grade 3	Confirm elevation, evaluate for potential causes (including but not limited to alcohol or other substance abuse, concomitant medications, reactivation of existing or de novo infection with hepatitis viruses) consult with BMS Medical Monitor or designate as soon as possible.
Grade 4	Interrupt all study medications, evaluate for potential causes (including but not limited to alcohol or other substance abuse, concomitant medications, reactivation of existing or de novo infection with hepatitis viruses), monitor values frequently and consult with BMS Medical Monitor or designate as soon as possible. If Grade 4 is deemed related to study medication the subject must be discontinued from the study. Otherwise, if reinstitution of study therapy is considered, please obtain approval from the BMS Medical Monitor or designate.

^a If persisting (> Grade 1/2), evaluate for alternative etiologies, including alcohol use and viral hepatitis

6.7.1.2 *Management of Renal Toxicity*

Serum phosphate levels and creatinine clearance (CrCl; CCL: as calculated by the Cockcroft Gault Equation [see [Appendix 4](#)] or eGFR) should be monitored and managed as described in the Viread local package insert/label.²⁹ Dose interval adjustments of TDF (Viread) are permitted, as described in [Section 4.5.2](#).

6.7.1.3 *Management of Hyperbilirubinemia*

Most patients taking ATV experience asymptomatic elevations in indirect (unconjugated) bilirubin related to inhibition of UDP-glucuronosyl transferase (UGT). Hepatic transaminase elevations that occur with hyperbilirubinemia should be evaluated for alternative etiologies. Dose modification of ATV is not permitted. Subjects who experience unacceptable jaundice/scleral icterus should be discussed with the BMS Medical Monitor or designate to determine if subjects are to be discontinued from study. The investigator must contact the BMS Medical Monitor or designate prior to discontinuing any subject due to hyperbilirubinemia.

6.7.1.4 *Gastrointestinal Toxicity Evaluation and Management Plan*

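### Section 4.5.2 makes the TDF interval adjustment for renal toxicity wait for an elective PK visit in control-arm subjects who opt in (minor)

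*Protocol*

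**What the plan says.** Section 4.5.2 bars dose and frequency changes for all assigned study drugs, with a single exception. When renal toxicity limits the use of TDF, its dosing interval may be adjusted according to the local label, but "only after the completion of the Week 2 Intensive PK optional Visit, if the subject is inclined to participate". The wording is the same in the original protocol and in Revised Protocol 01.

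Section 6.7.1.2 says that serum phosphate and creatinine clearance are to be monitored and managed as the local Viread label describes. On interval changes it adds: "Dose interval adjustments of TDF (Viread) are permitted, as described in" Section 4.5.2.

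On the visit itself, 3.1.3 says that subjects in all arms "will have the opportunity to participate in an elective Intensive PK Substudy visit at Week 2". It gives the expected size: "Approximately 60 subjects, 12 subjects from each arm, are expected to participate in the substudy". It adds that "BMS may allow the substudy to over-enroll in an effort to have a sufficient number of complete datasets". The only exclusion it states for the substudy is hemoglobin below 11.0 g/dL.

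Section 2.3 sets the general priority: "The rights, safety, and well-being of the study subjects are the most important considerations and should prevail over interests of science and society".

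**The concern.** The condition in 4.5.2 makes the availability of a safety measure depend on whether a research visit has been completed. The subjects concerned are control subjects (Arms 2 and 5) who have opted into the Week 2 intensive PK visit. If treatment-limiting renal toxicity is found in one of them before the visit, a site following the text cannot adjust the TDF interval while the subject stays in the substudy. Nothing in the protocol tells the site to take such a subject out of the substudy.

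What is at stake is a choice of remedy in a small group over a short period. The adjustment keeps TDF in a regimen that 1.1.1 describes as three fully active drugs, whereas interruption or stopping removes TDF for a time or for good.

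**Working it through.** The protocol gives no figure for this point, so the check is a reading of the sections together, followed by simple counts.

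**Does any section lift the condition?**
- 6.7.1.2 opens with label-based monitoring and management and attaches no PK timing to it. For interval adjustment, however, it sends the reader to 4.5.2, so the condition carries over.
- 3.1.3 does not exclude subjects with renal toxicity from the substudy.
- No other section does either. Read literally, the condition stands.

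**What does the delay protect?**
- 5.5.1 lists the intensive-PK analytes as BMS-955176, ATV, RTV and DTG. Tenofovir is not among them.
- Control subjects take no BMS-955176. The main stated use of their profiles is the comparison of DTG exposure with and without BMS-955176 on an ATV/RTV background, an exploratory objective in 1.3.3.
- Table 5.1-2 schedules no chemistry at the Week 2 visit, so waiting for it adds no renal information.

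**Which other routes are open?**
- Declining: the visit is elective (3.1.3), and the condition applies only to those who take part.
- Interruption: 4.5.2 does not bar it. 6.2.1 foresees it ("Follow-up is also required for nonserious AEs that cause interruption or discontinuation of study drug"), as does 6.3 ("Any laboratory test result abnormality that required the subject to have study drug discontinued or interrupted"), and 8.4 plans to tabulate interruptions. This is inferred from reporting rules; there is no interruption rule specific to renal toxicity.
- Stopping: 3.5 requires it when the investigator judges that an adverse event or laboratory abnormality makes continuation contrary to the subject's interest. TDF is a non-investigational product (4.2), and 3.5 leaves stopping such products to the investigator.
- Deviation: 9.1.1 allows one without prior ethics approval to eliminate an immediate hazard.

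**How many subjects does the condition cover?**
- Arm 2: about 12 of about 40, which is 12/40 = 30%.
- With Arm 5, if Stage 2 opens: 12 + 12 = 24 of about 80, again 30%; 24/200 = 12% of the whole trial.
- Over-enrolment would raise these counts. They are the subjects to whom the condition applies, not a forecast of toxicity. The protocol gives no event rate and none is assumed.

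**How long does it last, and would a scheduled test trigger it?**
- The visit window is Day 12-16 and the last sample is 24 hours after the first, so the visit is complete on Day 13-17 (by Day 16 if the window covers the whole profile).
- The next scheduled chemistry after Day 1 is at Week 4, within 5 days. Counting Week 4 as Day 28 or 29, the earliest date is Day 23 or 24.
- 23 − 17 = 6 and 24 − 17 = 7, so the first scheduled post-baseline chemistry falls at least 6-7 days after the condition has ended.
- Subjects with eGFR below 60 mL/min are excluded (3.3.2). In practice, only an unscheduled finding would bring the condition into play.

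**What would losing a profile cost?**
Section 8.4.4 says only that PK parameters are summarised by arm. Assume, for illustration, a t-based confidence interval for the DTG ratio on the log scale, Arm 1 against Arm 2. Its half-width is proportional to t(n1 + n2 − 2) × √(1/n1 + 1/n2).

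| Profiles | Width relative to 12 v 12, 90% interval | 95% interval |
|---|---|---|
| 12 v 11 | 1.0246 | 1.0253 |
| 12 v 10 | 1.053 | 1.055 |

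One unreplaced control profile widens such an interval by about 2.5%, and two by about 5.3-5.5%.

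**The case against.** The strongest reply is that the text already leads to the right outcome. The condition binds only a subject who wants to take part, the visit is elective, and a subject who needs an early adjustment simply forgoes it. Keeping the assigned regimen unchanged up to a PK profile is an ordinary substudy requirement, and the control regimen is the comparator in the DTG comparison. Section 6.7.1.2 also gives an unconditional instruction to manage renal function by the label. If safety can always be reached, 2.3 is not breached in practice.

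Much of this stands. Declining does free the subject, the clause will seldom apply, and the scientific purpose is genuine. What remains is that the protocol never states this way out. As written, 4.5.2 is a prohibition that a site could follow to the letter, and the unconditional sentence in 6.7.1.2 is followed by one that brings the condition back for this remedy.

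Three stronger readings are tempting, and the documents do not support them:
- A reader might infer that subjects with renal toxicity must stay on daily TDF until the visit. They need not, because the routes listed above remain open.
- A reader might infer that the clause withholds the mildest remedy. The label is not in the documents and is local, so neither its ranking of remedies nor what it would advise this early can be checked.
- A reader might take the 30% as the share of control subjects at risk of harm. It is only the share expected in the substudy.

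**Conclusion.** The point holds as a minor defect in a stated rule. For control-arm subjects who opt into the Week 2 visit, 4.5.2 puts the TDF interval adjustment behind an exploratory PK profile, and no section removes the condition. This reverses the order of priorities in 2.3, although no subject is left without a route to safety.

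The reach is small and the period short, and no efficacy endpoint is affected. The conclusion rests on a literal reading of 4.5.2. The counts rest on the expected 12 participants per arm and, for Arm 5, on Stage 2 opening. The confidence-interval figures rest on an interval that the protocol does not specify, and they bear only on the cost of the change.

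**What to change.** In 4.5.2, delete the closing condition ("only after the completion of the Week 2 Intensive PK optional Visit, if the subject is inclined to participate", with the conjunction before it). Add one sentence: a subject whose TDF interval is adjusted before the Week 2 visit does not take part in the intensive PK visit and may be replaced under the over-enrolment that 3.1.3 says the sponsor may allow. Section 6.7.1.2 then needs no change, since it refers to 4.5.2.

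Such a subject should not attend with the profile set aside afterwards. That would mean 12 blood draws from someone with renal toxicity for data left out of the comparison that justifies them.

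The cost is one deletion, one added sentence and an occasional lost control-arm profile. Replacement is at the sponsor's discretion; if it is granted, the number of profiles is preserved.
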